We are proposing a small randomized clinical trial in which 100 substance users will complete the existing Psychotherapy Development Center (PDC) pretreatment assessment battery as well as a novel battery of assays to evaluate cognitive-affective functioning. These batteries will be administered before and after the intervention (cognitive training tasks) to help examine the generalizability of any training effects to related cognitive training tasks (tasks that the participant was not specifically trained on). These related tasks will also help quantify participants' potential responsiveness to treatment and, as such, may help bridge the gap between behavior, mechanism, and treatment.

After completing pretreatment assessments, participants will be randomized to either a (1) cognitive remediation program (training tasks) specifically designed to address cognitive-affective dysregulation or (2) control tasks (verbal fluency tasks). Tasks will be completed twice per week for 4 weeks, after which assessment batteries will be repeated. Finally, we will evaluate real-world behavior and the durability of the training via a one-month follow-up, which will include assessment of substance use as well as the cognitive-affective battery. Our primary Specific Aim will be to evaluate the efficacy of the cognitive-remediation program relative to the control condition control on the indicators of cognitive-affective functioning and substance use, testing the hypothesis that individuals randomized to the cognitive remediation program will demonstrate improved functioning on the cognitive-affective battery as well as reduced substance abuse. We will also explore potential moderators of response to the training, including baseline measures of cognitive-affective function.

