Our long term goal is to enhance outcomes of effective 'top down' treatments like cognitive behavior therapy (CBT) and contingency management by combining them with brief 'bottom up' interventions that address, more directly, underlying mechanistic deficits that impact self-regulation and ultimately the maintenance of SUDs. The proposed research will lay the foundation for a more thorough evaluation of 'mechanism matched cognitive remediation' (1). Translation of these findings is expected to eventually allow clinician to match cognitive remediation interventions to the respective core deficits of their patients. Targeted intervention strategies such as these are likely to improve outcomes for multiple externalizing disorders, including SUDs. Moreover, as they are brief and administered via computer, the potential dissemination of these treatments could be more efficient, cost-effective, and implemented in a wider variety of settings (e.g., primary care, rural areas) than traditional behavior change interventions.

2. **Probable Duration of Project:** State the expected duration of the project, including all follow-up and data analysis activities.

Two years

3. **Background:** Describe the background information that led to the plan for this project. Provide references to support the expectation of obtaining useful scientific data.

Cognitive-Affective factors and substance use disorders (SUDs):

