4. **Research Plan:** Summarize the study design and research procedures using non-technical language that can be readily understood by someone outside the discipline. **Be sure to distinguish between standard of care vs. research procedures when applicable, and include any flowcharts of visits specifying their individual times and lengths.** Describe the setting in which the research will take place.

Overview:

The proposed SOBC supplement project will be conducted at the Substance Abuse Treatment Unit (SATU) and Adult Outpatient Psychiatric Services (IOP) in New Haven. One hundred substance

Version Date: 03022019

Version 3

users will be randomized, via a computerized urn randomization program (55) we have used in multiple previous trials (9, 10, 37, 56, 57) to either the cognitive remediation package or a control condition (computerized verbal fluency tasks), with trainings conducted twice per week for 4 weeks. Training will be conducted as an add-on to the participants' ongoing standard treatment at the clinic.

Several variables will be assessed. Demographic variables will include gender, race, and level of education. Person-specific variables will include type and severity of substance use disorder, personality characteristics, and treatment readiness. Pre- and post-training testing will evaluate change in cognitive-affective targets, with a one-month follow-up period to evaluate both the durability of training effects as well as impact on real-world behaviors (substance use).

This project will benefit the Parent award (P50 DA 0009241) by enabling us to evaluate how individuals with varying levels of these cognitive-affective deficits respond to study interventions and hence inform future projects which could address whether addressing these deficits via cognitive remediation improves response to empirically validated therapies via 'mechanism-matched' cognitive remediation.

Diagnostic and Baseline Assessments:

After providing written informed consent (see Human Subjects), participants will complete the following components of the Parent award (Psychotherapy Development Center, PDC) Core assessment battery to facilitate comparison with ongoing/previous Center studies:

- *Structured Clinical Interview for DSM-5 (SCID)* (58) (59), including antisocial personality disorder.
- The *Brief Symptom Index (BSI)* (60) is a widely used 53-item inventory of psychiatric symptoms.

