Participants will be randomized to one of 2 training conditions, to be completed twice per week over 4 weeks, *in addition* to standard treatment at SATU/IOP, which typically consists of weekly group meetings, case management and random urine toxicology screening. Each training session will be 30-45 minutes (time variability depends on speed of reading instructions and choices made in the tasks). Across all weeks the participant will complete approximately six hours of training.

Control condition. Participants randomized to this condition will complete a computerized verbal flexibility task (Text Twist). An active computer-based control was selected as it provides a rigorous comparison to intervention and will help address concerns that any game-style activities will produce improvements by controlling for computer time and game experiences, as well as non-specific elements such as support, attention, study contact, activation, and motivation. It is possible an active and engaging control condition may produce modest neurocognitive change in some domains, but available data indicate the control condition is not likely to influence the target-specific processes associated with self-regulation (75).

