Data will be collected, managed and analyzed through the standard procedures of the PDC as described in detail in the parent grant. Regarding statistical power, [name] previous study using a similar cognitive remediation battery (1) with 55 participants revealed an effect size of $d = .42$ for the malleability of performance on the training, with 92% power. A sample size of 100 will allow us to evaluate the effect of ongoing substance use as a moderator of treatment response at 80% power. We have established that we can recruit and treat a sample of this size in the one-year time allotment of the SOBC supplement. Our rates of end of treatment assessment and follow-up in Center trials is 90% or above, enabling us to conduct true intention to treat analyses with minimal statistical imputation (48, 49, 83). General Linear Modeling will be used to examine change in performance on these tasks over time. Using General Linear Modeling as we have in previous Center-supported studies (10, 37, 49, 57, 84), we will evaluate the extent to which participants who receive cognitive remediation show significantly greater improvement across time in the cognitive-affective assessment battery than those who receive the control training. Additionally, structural equation modeling (SEM) and latent profile analysis (LPA) will be used to examine variable-centered (correlation between measures) versus person-centered (profiles of individuals) alternatives. SEM with maximum-likelihood estimation will be used to test the association between pre-post measures and SUD-related behaviors. LPA, whereby each individual is assigned to a mutually exclusive assay class (i.e. profile) based on a data-driven analytic strategy, will be used to test the association between each individual's pre-post profile and treatment response. Moreover, we will use regression discontinuity analyses compare observations clustered closely on either side of a process-level threshold around a particular intervention. This analysis would allow us to examine the local average treatment effects on pre-post measures in a non-parametric data-driven manner.

Timeline	1	2	3	4	5	6	7	8	9	10	11	12
Recruit 3 participants/week	x	x	x	x	x	x	x	x	x			
Participant 100 completes 4 week treatment											x	
Participant 100 completes 1 month follow-up												x
Data analysis and preparation of reports												x

SECTION II: RESEARCH INVOLVING DRUGS, BIOLOGICS, RADIOTRACERS, PLACEBOS AND DEVICES

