Targeting Self-regulatory Deficits Through Cognitive Remediation Intervention

NCT03373240

September 1, 2017

Statistical power, data management and analysis

Data will be collected, managed and analyzed through the standard procedures of the PDC as described in detail in the parent grant. Regarding statistical power, [name] previous study using a similar cognitive remediation battery (1) with 55 participants revealed an effect size of $d = .42$ for the malleability of performance on the training, with 92% power. A sample size of 100 will allow us to evaluate the effect of ongoing substance use as a moderator of treatment response at 80% power. We have established that we can recruit and treat a sample of this size in the one-year time allotment of the SOBC supplement. Our rates of end of treatment assessment and follow-up in Center trials is 90% or above, enabling us to conduct true intention to treat analyses with minimal statistical imputation (48, 49, 83).

General Linear Modeling will be used to examine change in performance on these tasks over time. Using General Linear Modeling as we have in previous Center-supported studies (10, 37, 49, 57, 84), we will evaluate the extent to which participants who receive cognitive remediation show significantly greater improvement across time in the cognitive-affective assessment battery than those who receive the control training. Additionally, structural equation modeling (SEM) and latent profile analysis (LPA) will be used to examine variable-centered (correlation between measures) versus person-centered (profiles of individuals) alternatives. SEM with maximum-likelihood estimation will be used to test the association between pre-post measures and SUD-related behaviors. LPA, whereby each individual is assigned to a mutually exclusive assay class (i.e. profile) based on a data-driven analytic strategy, will be used to test the association between each individual's pre-post profile and treatment response. Moreover, we will use regression discontinuity analyses compare observations clustered closely on either side of a process-level threshold around a particular intervention. This analysis would allow us to examine the local average treatment effects on pre-post measures in a non-parametric data-driven manner.

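### The planned regression discontinuity analysis cannot deliver the local average treatment effects it promises, because training is assigned by randomisation and not by a score

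*Protocol*

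**What the plan says.** Protocol section 13 (Statistical Considerations) and the SAP (Statistical power, data management and analysis) carry the same two sentences. The first says that "we will use regression discontinuity analyses compare observations clustered closely on either side of a process-level threshold around a particular intervention". The second gives the aim: "This analysis would allow us to examine the local average treatment effects on pre-post measures in a non-parametric data-driven manner". Neither document names the score, the cut-off, the window, or any rule that links the threshold to receiving training. Both refer general procedures to a parent grant that is not part of the file.

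Assignment is described three times in the Protocol, always as randomisation:
- Section 1, Statement of Purpose: "After completing pretreatment assessments, participants will be randomized to either a (1) cognitive remediation program" or to control tasks.
- Section 4, Overview: the substance "users will be randomized, via a computerized urn randomization program".
- Section 4, Interventions: "Participants will be randomized to one of 2 training conditions, to be completed twice per week over 4 weeks".

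Two further statements bear on what the analysis might be for. Section 1 adds that "We will also explore potential moderators of response to the training, including baseline measures of cognitive-affective function". The Overview in section 4 expects the project to help the parent award by "enabling us to evaluate how individuals with varying levels of these cognitive-affective deficits respond to study interventions". Neither is tied to the regression discontinuity analysis.

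**The concern.** Regression discontinuity was built for settings where a score decides who is treated. People just above and just below the cut-off are alike except for treatment, so a jump in the outcome can be attributed to treatment. In this trial people on either side of a baseline threshold have the same chance of training, so comparing the two sides contains no treatment contrast.

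What is at stake is interpretation. If the result is reported under the label the documents give it, a null jump could be read as no local training effect when the effect is large, and a non-null jump could be read as the training effect when it is something else. The question the trial does pose, how response varies with baseline function, would not be answered by this analysis.

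**Working it through.** The documents give no effect size, power or alpha for this analysis, so there is no stated figure to reproduce. The check is one of identification, followed by an illustration.

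**1. Identification.** Let c be the cut-off, p(x) the chance of training at score x, m0(x) the mean outcome under control, and τ(x) the training effect.

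- Regression discontinuity effect = (jump in mean outcome at c) / (jump in p at c).
- Jump in mean outcome = [m0(c+) − m0(c−)] + [p(c+)τ(c+) − p(c−)τ(c−)].
- Under randomisation p(c+) = p(c−) = p. The denominator is zero, and the numerator becomes [m0(c+) − m0(c−)] + p[τ(c+) − τ(c−)].

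If the control outcome has no step at c and τ is continuous there, the numerator is zero however large τ is. If τ steps at c, the numerator is p times the step. With p = 0.5 (1:1 allocation, assumed; the ratio is not stated), steps of 0.42, 0.84 and 1.0 SD give 0.21, 0.42 and 0.50.

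**2. Can any feature of the design supply a jump in p?**
- Urn randomisation: the balancing variables are not stated, but balancing works towards equal arms within levels and creates no jump.
- The Shipley IQ limit of 70 (section 8): it decides entry, not arm, and there are no outcomes below it.
- A threshold on a post-training score: it is measured after assignment and cannot determine it.
- Matching training to deficits: section 1 presents this as an eventual use of the findings, not as a rule in this trial.

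**3. Illustration.** From the documents: 100 randomised; 90 analysed as the lower case, since section 13 expects assessment rates of 90% or above. Assumed: x standard normal, cut-off 0, outcome = 0.5x + arm × τ(x) + error with variance 1 − 0.5² = 0.75, 1:1 arms, two-sided 5% tests, local linear fit with separate slopes in a ±1 SD window (about 68 or 61 people used), 4,000 runs. The 0.42 is borrowed from the effect size in section 13 as one illustrative value only; there it describes malleability of performance on the training, not an arm difference.

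| True training effect | Mean pooled jump, 100 (90) | Significant, 100 (90) |
|---|---|---|
| Constant 0, 0.42, 0.5 or 1.0 SD | within 0.015 of 0 (same) | about 5% (about 5%) |
| Rising 0.3 SD per SD of score | within 0.015 of 0 (same) | about 5% (about 5%) |
| Step of 0.42 SD | 0.21 (0.22) | 8% (8%) |
| Step of 0.84 SD | 0.42 (0.42) | 16% (15%) |
| Step of 1.0 SD | 0.49 (0.51) | 19% (19%) |

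This is not a small-sample effect. With 100,000 people, a ±0.5 SD window and randomised training, true effects of 0, 0.42 and 1.0 SD gave mean jumps of 0.000, −0.004 and 0.000. When the cut-off itself assigned training, the same estimator gave 0.000, 0.421 and 0.997.

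**4. What randomisation does support, same model.** ANCOVA of the arms: SE = √0.75 × 2/√100 = 0.173, so a 0.5 SD effect lies 0.5/0.173 = 2.89 SE from zero. The simulation gave a mean of 0.50 with about 81% power (76–77% with 90).

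**5. Conditions on the zero and half-step results.** They are limit results. With no training effect but a 0.5 SD step in the control outcome, the mean jump was about 0.50. With a smooth but steep effect, τ(x) = 1/(1 + exp(−6x)), it was about 0.17 in the ±1 SD window. Neither figure is the training effect at the threshold, so these cases add to the risk of misreading.

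**The case against.** The strongest reply is that neither document says the arms are pooled. The phrase about a particular intervention could mean a discontinuity fitted within each arm and then contrasted. That version does recover a step in the effect: with 100 analysed, a 1.0 SD step returned about 1.0 and a 0.42 SD step 0.42. Power, however, was about 21% and 7%, and the quantity is a difference in effect across the threshold. The promised treatment effect is still not estimated. An ordinary comparison of arms near a threshold would be valid, but it is a randomised subgroup or interaction analysis under another name.

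It is also fair to say that this analysis comes last in the plan, that the harm depends on how the result is read, and that the numbers rest on assumed correlations, windows and effects. All of this stands. It limits the severity without rescuing the method, because the argument in step 1 does not need the numbers.

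Some stronger readings are tempting and are not supported:
- That the jump is always zero. This holds only under the conditions in step 5.
- That the sponsor plans to search the data for a threshold. The text calls the approach non-parametric and data-driven, but describes no search.
- That the hope to "match cognitive remediation interventions to the respective core deficits of their patients" implies a stepped effect. It says nothing about the shape of the effect.
- That the score and cut-off are defined nowhere. They are absent from these two documents; the parent grant cannot be seen. Its general procedures would not change how this trial assigns training.

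**Conclusion.** The concern holds. As written, the method and the promised estimand do not fit a randomised assignment. Pooled over arms, with no control step and local linearity, the expected jump is about zero for a constant or linearly varying effect, and about half of any step under assumed 1:1 allocation; another ratio changes the half but not the zero. Fitted by arm, the analysis estimates a difference in effect, with very low power. The identification argument rests only on how the documents say training is assigned; the simulated sizes rest on the stated assumptions.

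A reader might infer that the trial's efficacy conclusion is compromised. It is not: the general linear model comparison of the randomised arms does not depend on this analysis. The plan should be corrected, but this is at most a should-fix point.

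**What to change.** In both Protocol section 13 and the SAP, delete the two regression discontinuity sentences, including the local average treatment effect claim. Replace them with an interaction between arm and a continuous baseline (pre-training) process score in the general linear model, adjusted for the baseline outcome score. This serves the moderator aim in section 1. List the scores before outcome data are examined by arm, report estimates with 95% intervals, and label the tests exploratory.

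If a threshold comparison was intended, name the score and cut-off before outcome data are examined by arm, and write it as a randomised arm-by-threshold interaction rather than regression discontinuity.

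Confirm also that the baseline battery is completed before randomisation. Section 1 says so, but the study assessments schedule in section 4 marks urn randomisation at Screen and the n-back, BART and delay discounting tasks at Week 0. The two should be reconciled, so that the moderator scores are known to precede assignment.

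The cost is wording changes in two documents and no new data. Power is low. With SE = √0.75/√(100/4) = 0.173, a slope of 0.3 SD per SD of score lies 1.73 SE from zero, giving about 40% power with 100 analysed; with 90 it is about 35%. The results would be hypothesis-generating only.

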Targeting Self-regulatory Deficits Through Cognitive Remediation Intervention

NCT03373240

September 1, 2017

Statistical power, data management and analysis

Data will be collected, managed and analyzed through the standard procedures of the PDC as described in detail in the parent grant. Regarding statistical power, [name] previous study using a similar cognitive remediation battery (1) with 55 participants revealed an effect size of $d = .42$ for the malleability of performance on the training, with 92% power. A sample size of 100 will allow us to evaluate the effect of ongoing substance use as a moderator of treatment response at 80% power. We have established that we can recruit and treat a sample of this size in the one-year time allotment of the SOBC supplement. Our rates of end of treatment assessment and follow-up in Center trials is 90% or above, enabling us to conduct true intention to treat analyses with minimal statistical imputation (48, 49, 83).

General Linear Modeling will be used to examine change in performance on these tasks over time. Using General Linear Modeling as we have in previous Center-supported studies (10, 37, 49, 57, 84), we will evaluate the extent to which participants who receive cognitive remediation show significantly greater improvement across time in the cognitive-affective assessment battery than those who receive the control training. Additionally, structural equation modeling (SEM) and latent profile analysis (LPA) will be used to examine variable-centered (correlation between measures) versus person-centered (profiles of individuals) alternatives. SEM with maximum-likelihood estimation will be used to test the association between pre-post measures and SUD-related behaviors. LPA, whereby each individual is assigned to a mutually exclusive assay class (i.e. profile) based on a data-driven analytic strategy, will be used to test the association between each individual's pre-post profile and treatment response. Moreover, we will use regression discontinuity analyses compare observations clustered closely on either side of a process-level threshold around a particular intervention. This analysis would allow us to examine the local average treatment effects on pre-post measures in a non-parametric data-driven manner.
